7.4 Non-Compartmental Analysis

The following configuration for the NCA of CD388 in plasma or nasopharyngeal concentrations (with Phoenix® WinNonlin® version 8 or higher) will be used:

- Data: Serial sampled data
- Model/Dose options Type: Plasma (200 -202) / Extravascular
- AUC Calculation Method: Linear Up/Log Down
- Lambda Z (λ_z) calculation: Best fit method for λ_z Linear-Log regression

Reasons for excluding PK parameters will include the following:

- AUC: AUC parameters will not be estimated if less than 3 consecutive measurable concentrations are observed.

PK parameters requiring λ_z estimation (e.g., and $t_{1/2}$) will be set to Not Reported (NR) in the Tables and Listings if they meet the following:

- $R^2 < 0.8$

The PK parameters for CD388 are presented in [Table 5](#).

Table 5: Pharmacokinetic Parameters of CD388 in Plasma

PK Parameter	Definition
Plasma Concentrations	
C_{max}	Maximum observed concentration
t_{max}	Time of maximum observed concentration; if it occurs at more than one time point, T_{max} is defined as the first time point with this value
AUC_{0-t}	Area under the concentration time curve from time 0 (dose administration) to the time of last quantifiable concentration (t_{last})
$AUC_{0-\infty}$	Area under the concentration time curve extrapolated to infinity, calculated as $AUC_{0-t} + C_{LQC}/\lambda_z$, where C_{LQC} is the measured concentration at time t_{last} and λ_z is the apparent elimination rate constant, estimated by linear regression of the terminal linear portion of the log concentration versus time curve
$t_{1/2}$	Terminal elimination half-life, calculated as $\ln(2)/\lambda_z$
CL/F	Apparent total clearance, calculated as Dose/ $AUC_{0-\infty}$
V_z/F	Apparent volume of distribution, calculated as Dose/ $\lambda_z * AUC_{0-\infty}$
Nasopharyngeal Concentrations	
C_{max}	Maximum observed concentration
t_{max}	Time of maximum observed concentration
AUC_{0-t}	Area under the concentration time curve from time 0 (dose administration) to the time of last quantifiable concentration (t_{last})
Plasma Concentrations	
The following plasma PK parameters will be used for PK calculation and presented in the listings only	
$AUC_{\%ext}$	Extrapolated area (i.e. percentage of $AUC_{0-\infty}$ due to extrapolation from t_{last} to infinity)
R^2	Goodness of fit statistic for the terminal elimination phase
Number of Points	Number of data points in computing λ_z
λ_z Lower	Lower limit on time for values included in the calculation of λ_z
λ_z Upper	Upper limit on time for values included in the calculation of λ_z
λ_z	Apparent elimination rate constant, estimated by linear regression of the terminal linear portion of the log concentration versus time curve
t_{last}	Time of last measurable observed concentration

7.5 Statistical Methodology

All tables, figures, and listings (TFLs), when appropriate, will be summarized by cohort and by injection route.

7.5.1 Summary Statistics

Summary statistics of the individual concentration data and derived parameters will be calculated for the PK population at each nominal time point and for all PK parameters. Concentration data will be summarized by group using the following statistics: number of observations (N), arithmetic mean (mean), standard deviation (SD), minimum (min), median, maximum (max), and coefficient of variation (CV%). PK parameters will be summarized using these same statistics, as well as geometric mean and geometric mean CV%.

7.5.2 Statistical Analysis

The natural logarithmic transformation of C_{max} , AUC_{0-t} , and $AUC_{0-\infty}$ will be used for all statistical inference. Individual ratios of untransformed parameter values will also be presented as part of the descriptive analysis.

Pharmacokinetic parameters (C_{max} , AUC_{0-t} , and $AUC_{0-\infty}$) will be statistically analyzed using an Analysis of Variance (ANOVA) model by dose level. The fixed factors included in this model will be injection route (IM to SQ). The 90% confidence interval (CI) for the exponential of the difference in least squares means (LSmeans) between each comparison of interest (IM to SQ) will be calculated.

Pharmacokinetic parameters (C_{max} , AUC_{0-t} , and $AUC_{0-\infty}$) will be statistically analyzed using an Analysis of Variance (ANOVA) model to assess relative bioavailability. Dose is the fixed factor. The 90% CI for the differences in LSmeans for each pairing of doses will be calculated and used to assess relative bioavailability. Injection route (IM and SQ) will be assessed in two separate models.

Pharmacokinetic parameters (C_{max} , AUC_{0-t} , and $AUC_{0-\infty}$) for IM and SQ cohorts will also be assessed statistically for dose proportionality, using a power model:

$$\ln(\text{PK parameter}) = \alpha + \beta \cdot \ln(\text{Dose}) + \varepsilon$$

where α is the intercept, β is the slope and ε is the error term.

A point estimate and corresponding 90% CI will be derived for the slope (β).

T_{max} will be analyzed descriptively.

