6. STUDY DESIGN

6.1. Description of the Study

This is a FIH, Phase 1, single-center, prospective, randomized, double-blind study of ascending single doses of CD388 Injection administered IM or SQ to healthy adult subjects followed by another single dose of CD388 Injection administered by the same route 3 months or 5 effective half-lives, whichever is longer, after the first dose in the middle and high dose groups (dosing may be adjusted for tolerability). The goals are to assess safety, tolerability, immunogenicity (anti-drug antibodies [ADA]), and PK of CD388.

Dose levels of CD388 to be assessed will follow an ascending single dose design with the starting dose based on findings from 3-month rat and monkey toxicology studies. Within each route (IM and SQ dose, route assignment is unblinded), subjects will be randomized to receive a single dose of CD388 Injection or saline placebo (treatment assignment is blinded) according to the design in [Table 5](#). It should be noted that each cohort will be divided into 2 groups identified as “sentinel” groups (randomized 1:1) and “main” groups (randomized 7:2):

- Low dose (50 mg) level: Cohort 1A (IM) and Cohort 1B (SQ) – each route n = 2 sentinel and n = 9 main
- Mid dose (150 mg) level: Cohort 2A (IM) and Cohort 2B (SQ) – each route n = 2 sentinel and n = 9 main
- High dose (450 mg) level: Cohort 3A (IM) and Cohort 3B (SQ) – each route n = 2 sentinel and n = 9 main
- Highest dose (900 mg) level: Cohort 4B (SQ) – n = 2 sentinel and n = 9 main

For each route, the sentinel or first group of 2 subjects (1 CD388: 1 placebo) at a dose level will be administered blinded study drug and closely monitored for safety for at least 1 week. The Principal Investigator (PI) and Sponsor will review blinded safety data after the initial sentinel group subjects at a dose level have completed dosing and followed for a minimum of 1 week. If no drug-related SAEs or drug-related Grade ≥ 3 AEs have occurred, the subjects in the corresponding main group may be dosed within 24 hours. The observation duration may be adjusted for the sentinel groups in Cohorts 2A, 2B, 3A, 3B, and 4B based on data from previous cohorts.

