6.6. Method of Treatment Assignment and Blinding

After informed consent has been obtained, subjects will be screened for study eligibility before randomization.

Within each route (IM and SQ dose, route assignment is unblinded), subjects will be randomized to receive a single dose of CD388 Injection or saline placebo (treatment assignment is blinded). The study site's pharmacist (or pharmacist designee) will obtain the study drug assignment via an Interactive Response Technology (IRT) or by a manual paper transaction. A subject is considered randomized when a randomization transaction is recorded in the IRT or the subject's source documents if performed manually.

All blinded study personnel (including the Sponsor, Investigator, and site personnel directly involved in study conduct) and subjects will remain blinded to study drug assignment until the study is completed and the final database is locked with the exception of the unblinded pharmacy personnel, pharmacy monitor, and unblinded Sponsor personnel (such as Data Review Committee, clinical supply manager, PK lead, and quality manager) who may be unblinded to study medication at any time during study conduct. The pharmacy monitor will monitor study drug preparation and accountability during the study and cases in which unblinding is required due to a safety or tolerability issue. To maintain study blinding, study drug preparation will be

performed by an unblinded site pharmacist (or qualified unblinded personnel at the study site not involved with study procedures or evaluations).

Instructions for study drug preparation and dosing are outlined in the Pharmacy Manual provided separately to the site. In the case of a medical emergency requiring the Investigator to know the identity of the study drug, the Investigator will follow the procedures outlined in [Section 8.4](#).

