6 DEMOGRAPHIC AND OTHER BASELINE CHARACTERISTICS

Unless otherwise specified, all available data will be listed for the safety population as detailed in [Table 4](#). Summary tables for demographics and other baseline characteristics by injection route (IM or SQ), CD388 dose, and pooled placebo will be presented for safety and PK populations.

Table 4: Data Presentations for Demographic and Other Baseline Characteristics

Data	Variables	Presentation
Demographic and other baseline characteristics	Sex, age, ethnicity, race, height (cm), weight (kg) and body mass index (BMI, kg/m ²)	Listing and summary tables
Medical history	All medical history findings	Listing Note: includes coded terms (system organ class [SOC] and preferred term [PT])
Prior medications	All medications taken 30 days prior to study drug administration and concomitant medications (including vaccines, prescription medications, nonprescription medications, dietary supplements, vitamins, or herbal medications)	Listing Note: includes coded terms (anatomic therapeutic chemical [ATC] level 4 and preferred name)

Demography and baseline characteristics will be summarized using descriptive statistics.

The medical history at screening will include all queries by the medical and clinical staff related to the subject's well-being and history of relevant past medical events/experiences. Medical history will be coded to Medical Dictionary of Regulatory Activities (MedDRA) terms version 24.1 and listed by subject.

Prior medication will be coded using the World Health Organization Drug Dictionary Global B3 Sept 1, 2021, and will be listed by subject.

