			N Mean SD Min Median Max CV% GeoMean GeoMean CV%					
NC: Not Calculated								

x = 1 through 8 for Cohorts 1A, 1B, 2A, 2B, 3A, 3B, and 4B and PK Completer Population (Cohorts 2A, 2B, 3A and 3B only)
 <DOSE> = 50 mg, 150 mg, 450 mg and 900 mg for Cohorts 1A/1B, 2A/2B, 3A/3B, and 4B, respectively.
 <ADMIN> = Intramuscular Injection for Cohorts 1A, 2A, and 3A or Subcutaneous Injection for Cohorts 1B, 2B, 3B, and 4B.
 <COHORT> = Cohorts 1A, 1B, 2A, 2B, 3A, 3B, and 4B.

Programming Note:

Table 14.2.1.2.2.x: "Descriptive Statistics of Plasma CD388 Pharmacokinetic Parameter Estimates Following a Repeated Single <ADMIN> of <DOSE> CD388 to Healthy Subjects (<COHORT>)" will follow the same layout.

Table 14.2.2.2.1.x: "Descriptive Statistics of Nasopharyngeal CD388 Pharmacokinetic Parameter Estimates Following a Single <ADMIN> of <DOSE> CD388 to Healthy Subjects (<COHORT>)" will follow the same layout.

Table 14.2.2.2.2.x: "Descriptive Statistics of Nasopharyngeal CD388 Pharmacokinetic Parameter Estimates Following a Repeated Single <ADMIN> of <DOSE> CD388 to Healthy Subjects (<COHORT>)" will follow the same layout.

Table 14.2.8 Template T2.3: PK Parameters Assessment of CD388 for <Cohort> SQ relative to IM – (Pharmacokinetic Population)

Table 14.2.3.1
 Statistical Analysis of Plasma CD388 Pharmacokinetic Parameters Between IM and SQ Administration
 (PK Population)

Dose	Parameter (unit)	n	Geometric LSmeans [1]		SQ/IM Ratio (%)	90% Confidence Interval (%)	
			IM Route	SQ route		Lower Bound	Upper Bound
xx mg	C_{\max} (unit)	xxx	xxxxxx	xxxxxx	xxx	xxx	xxx
	AUC_{0-t} (unit)	xxx	xxxxxx	xxxxxx	xxx	xxx	xxx
	$AUC_{0-\infty}$ (Unit)	xxx	xxxxxx	xxxxxx	xxx	xxx	xxx
...							
Date: VERSION – YYYY-MM-DD			Data Source: XXXX			Program Source: XXXXX.sas	

IM = Intramuscular(Reference); SQ = Subcutaneous(Test)

[1] Geometric Least Square (LS)means are based on the exponential of LSmeans of ln-transformed values
 Note(s):

An analysis of variance (ANOVA) was performed on the ln-transformed parameters with the following fixed factors: Injection route.

The ratio and 90% confidence interval (CI) were obtained by exponentiating the resulting difference between each comparison of interest (IM to SQ) least-squares means and its corresponding 90% CI.

Table 14.2.10 **Template T2.4: Dose Proportionality Analysis – (Pharmacokinetic Population)**

Table 14.2.4.1
 Dose Proportionality Analysis of Plasma CD388 Pharmacokinetic Parameters
 (PK Population)

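### The IM versus SQ exposure comparison (8 versus 8 at each dose) leaves out body weight; one weight-adjusted model would tighten it at little cost

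*SAP*

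**What the plan says.** **Model.** In SAP 7.5.2 the log-transformed exposure parameters "will be statistically analyzed using an Analysis of Variance (ANOVA) model by dose level". Route is the only factor: "The fixed factors included in this model will be injection route (IM to SQ"). The footnote to the shell for Table 14.2.3.1 repeats this: "An analysis of variance (ANOVA) was performed on the ln-transformed parameters with the following fixed factors: Injection route". The result is a ratio with an interval: "The 90% confidence interval (CI) for the exponential of the difference in least squares means (LSmeans"). The ANOVA for dose pairings and the power model in the same section carry no weight term either.

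**Size.** Protocol 6.1 plans, at 50, 150 and 450 mg, "each route n = 2 sentinel and n = 9 main". Sentinel groups are randomised 1:1 and main "groups (randomized 7:2"). SAP 4 keeps placebo subjects out of the PK population. The 900 mg level has an SQ cohort only.

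**Allocation.** Protocol 6.6 states: "Within each route (IM and SQ dose, route assignment is unblinded), subjects will be randomized to receive a single dose" of CD388 or placebo. Protocol 6.1 and SAP 3.4 agree.

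**Weight.** SAP 6, Table 4 lists "height (cm), weight (kg) and body mass index" among the baseline characteristics, and these are to be tabulated for the PK population. Protocol 7.1 restricts BMI but not weight, and Protocol 8.1.3 rules out individual dose adjustment. Protocol 12.4 leaves a population PK analysis optional, reports it separately and names no covariates.

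**The concern.** With a fixed mg dose, heavier subjects can be expected to have lower exposure. Weight is then a source of between-subject spread that could be removed from the SQ/IM ratio using data already collected. A route-only model leaves it in the residual. Each dose also estimates its own variance from 16 subjects, although seven cohorts could contribute.

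Allocation is a separate matter. Randomisation, as described, decides between CD388 and placebo after the route is fixed. Nothing in the design therefore prevents one route's cohort from being heavier for reasons of recruitment. A route-only model cannot tell such a difference from an effect of route. At stake is how the SQ/IM ratio is read. It serves the secondary PK objective.

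**Working it through.** **Inputs from the documents.** CD388 subjects per cohort: 1 sentinel + 7 main = 8. Cohorts: 3 IM and 4 SQ. Check: 7 x 8 = 56 on CD388 and 7 x 11 = 77 enrolled, which match the protocol. The documents give no CV, CI width, margin or power for this comparison, so there is no precision figure to reproduce.

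**Assumed inputs.** Between-subject CV 30% (range 20-50%), SD of ln(weight) s_w = 0.15-0.20, exponent of exposure on weight b = 0.5-1.0. I also assume one dosing period and no dropouts; SAP 7.5.2 does not say which dosing period feeds the model.

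**1. Planned interval.** sigma = sqrt(ln(1 + 0.30²)) = sqrt(0.0862) = 0.294. SE of the log ratio = 0.294 x sqrt(2/8) = 0.147. With t(0.95; 14) = 1.761, the 90% CI around a true ratio of 100% is exp(±1.761 x 0.147) = 77-130%. At other CVs:

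| CV | 90% CI, 8 versus 8 |
|---|---|
| 20% | 84-119% |
| 40% | 71-140% |
| 50% | 66-152% |

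**2. Is chance weight imbalance already inside this interval?** The SD of the shift in the log ratio due to weight is b x s_w x sqrt(2/8).

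- Low corner: 0.5 x 0.15 x 0.5 = 0.0375, a shift of about 4%.
- High corner: 1.0 x 0.20 x 0.5 = 0.10, a shift of about 10%.

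The total variance of the log ratio is 0.0862 x 0.25 = 0.0215. The weight part is 0.0014 to 0.0100 of that total and is not added to it. Simulating 8 versus 8 under these assumptions gives coverage of about 90% for the planned interval in every scenario. The 4-10% shift and the width of the interval are therefore the same harm, counted once.

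**3. Gain from one ANCOVA.** Residual df = 56 - 7 cells - 1 slope = 48, and t(0.95; 48) = 1.677. The expected half-width relative to the plan is the product of four factors:

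- t ratio: 1.677 / 1.761 = 0.952.
- Mean of the estimated SD, about 1 - 1/(4 df): 0.995 at 48 df over 0.982 at 14 df = 1.013.
- Cost of estimating the slope: sqrt(1 + 1/47) = 1.011.
- Variance removed: sqrt(1 - R²), with R² = (b x s_w)² / sigma².

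The first three multiply to 0.975.

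| Case | R² | sqrt(1 - R²) | Relative half-width |
|---|---|---|---|
| No weight effect | 0 | 1 | 0.975 |
| b = 0.5, s_w = 0.15 | 0.0056/0.0862 = 0.065 | 0.967 | 0.943 |
| b = 0.75, s_w = 0.175 | 0.0172/0.0862 = 0.20 | 0.894 | 0.872 |
| b = 1.0, s_w = 0.20 | 0.0400/0.0862 = 0.464 | 0.732 | 0.714 |

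Simulation of the seven-cell model agrees: reductions of about 2%, 6%, 13% and 28%, with coverage about 90%. With no weight effect, the 5th-95th percentile of the log half-width also tightens, from 0.18-0.33 to 0.21-0.29.

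**4. A systematic difference.** As an illustration only, suppose one cohort averages 85 kg and the other 75 kg. Exposure in the heavier cohort would be (85/75)^-b, or 94% at b = 0.5 and 88% at b = 1.0. A route-only model would attribute that to route.

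**The case against.** The strongest reply is that the planned analysis is valid and the gain is a matter of preference. Much of this stands.

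- A reader might infer that the planned interval is wrong, or that chance weight imbalance biases the ratio beyond its CI. Step 2 shows otherwise. Only a systematic difference would escape the interval. The documents give no evidence of one, and all cohorts recruit at a single centre under the same criteria.
- A reader might expect the interval to shrink by a factor of about 1.8. That figure belongs to a different model, which pools 24 versus 24: sqrt(24/8) x 1.761/1.680 = 1.8. It assumes the same route ratio at every dose. The model proposed here still contrasts 8 with 8 at each dose.
- The comparison is secondary. The protocol plans no formal tests and sets no acceptance range for the ratio, and the sample size follows first-in-human convention. Weight will be tabulated by route and dose, so an imbalance would be visible.
- The assumed exponent range is a clearance argument. It bears on AUC more directly than on Cmax.
- Allocation to route is not entirely clear. Protocol 8.1 and the synopsis use looser wording that ties route and dose to the subject's randomisation. Protocol 6.1, 6.6 and SAP 3.4 are the more specific texts, and none describes random allocation to route.

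These points limit the importance of the matter. They do not remove the precision gain, and an optional population PK analysis with no named covariates does not replace the adjustment.

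**Conclusion.** The point holds as a cheap improvement to a secondary, descriptive comparison. It does not identify a defect in validity. With route as the only term, the SQ/IM interval is wider than the available data require: by about 6-28% in half-width at CV 30% over the assumed weight effects, and by about 2% if weight has none. The documents supply no CV, weight distribution or exponent, so these sizes rest on assumptions. Most of the imprecision comes from having 8 subjects per cohort, and no choice of model removes that. The second benefit is protection of interpretation: since no random allocation to route is described, adjustment would separate a systematic weight difference from the route effect. It would not deal with other differences between the cohorts.

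**What to change.** In SAP 7.5.2, make the main route analysis one ANCOVA over all CD388 cohorts: ln(parameter) = dose-by-route cell + ln(baseline weight), with common residual variance (48 df). Report the SQ/IM ratio and 90% CI at 50, 150 and 450 mg from it. The cell structure does not assume a constant route ratio. Add ln(weight) to the power model. Keep the unadjusted by-dose ANOVA as a sensitivity analysis. State that route comparisons are between cohorts with no described random allocation to route, and reconcile the wording of Protocol 8.1 with 6.6.

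The cost is SAP text, one model and a revised table shell; no new data are needed. The statistical downsides should be named:

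- One degree of freedom goes to weight.
- One weight slope is assumed across routes and doses.
- Log-scale variance is assumed equal across cohorts whose sampling and follow-up differ. Cohorts 3A and 4B omit the 2 h and 4 h samples. Follow-up ends at Day 120 for 1A and 1B, at about four half-lives for the first dose in Cohorts 2 and 3, and at Day 206 for 4B. This matters most for AUC0-t, so the residual spread should be checked by cohort.

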Route	Parameter (Unit)	n	Estimate of	Estimate of	90% Confidence Interval of Slope	
			Intercept (α)	Slope (β)	Lower Bound	Upper Bound
IM						
	C_{\max} (Unit)	xxx	xxx	xxx	xxxxx	xxxxx
	AUC_{0-t} (Unit)	xxx	xxx	xxx	xxxxx	xxxxx
	$AUC_{0-\infty}$ (Unit)	xxx	xxx	xxx	xxxxx	xxxxx
SQ						
	C_{\max} (Unit)	xxx	xxx	xxx	xxxxx	xxxxx
	AUC_{0-t} (Unit)	xxx	xxx	xxx	xxxxx	xxxxx
	$AUC_{0-\infty}$ (Unit)	xxx	xxx	xxx	xxxxx	xxxxx

Date: VERSION – YYYY-MM-DD

Data Source:

Program Source: XXXXX.sas

XXXX

IM = Intramuscular; SQ = Subcutaneous

Note: Proportionality analysis was performed using a power model: $\ln(\text{PK parameter}) = \alpha + \beta \times \ln(\text{dose}) + \text{error}$, with β as slope.

Table 14.2.5.1
 Summary of Positive Anti-drug Antibodies Titer
 (Safety Population)

IM Route				SQ Route				
CD388 50 mg (N = XX)	CD388 150 mg (N = XX)	CD388 450 mg (N = XX)	Pooled Placebo (N = XX)	CD388 50 mg (N = XX)	CD388 150 mg (N = XX)	CD388 450 mg (N = XX)	CD388 900 mg (N = XX)	Pooled Placebo (N = XX)
n (%)	n (%)	n (%)	n (%)	n (%)	n (%)	n (%)	n (%)	n (%)
Positive ADA xx (xx.x)	xx (xx.x)	xx (xx.x)	xx (xx.x)	xx (xx.x)	xx (xx.x)	xx (xx.x)	xx (xx.x)	xx (xx.x)

Date: VERSION - YYYY-MM-DD

Data Source: XXXX

Program Source: XXXXX.sas

IM = Intramuscular; SQ = Subcutaneous.

Notes: Percentages are based on the number of subjects in the Safety population (N).

Table 14.2.6.1
 Relative Bioavailability Analysis of Plasma CD388 Pharmacokinetic Parameters
 (PK Population)

Route	Parameter (Unit)	n	LSMeans		Dose 1/Dose 2 Difference	90% Confidence Interval of Difference	
			Dose 1	Dose 2		Lower Bound	Upper Bound
IM							
	C _{max} (Unit)	xxx	xxx	xxx	xxx	xxxxx	xxxxx
	AUC _{0-t} (Unit)	xxx	xxx	xxx	xxx	xxxxx	xxxxx
	AUC _{0-∞} (Unit)	xxx	xxx	xxx	xxx	xxxxx	xxxxx
SQ							
	C _{max} (Unit)	xxx	xxx	xxx	xxx	xxxxx	xxxxx
	AUC _{0-t} (Unit)	xxx	xxx	xxx	xxx	xxxxx	xxxxx
	AUC _{0-∞} (Unit)	xxx	xxx	xxx	xxx	xxxxx	xxxxx

Date: VERSION - YYYY-MM-DD

Data Source: XXXX

Program Source: XXXXX.sas

IM = Intramuscular; SQ = Subcutaneous

Note: ANOVA model includes dose as fixed factor.

Table 14.2.13 Template T3.1: Treatment-Emergent Adverse Events (TEAEs) - Overall Summary (Safety Population)

Table 14.3.1.1
 Treatment-Emergent Adverse Events (TEAEs) - First Dose - Overall Summary
 (Safety Population)

	IM Route					SQ Route				

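### The between-dose relative bioavailability ANOVA is not dose-normalised, so every contrast carries the known constant ln(Dose 1/Dose 2)

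*SAP*

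**What the plan says.** SAP section 7.5.2 uses natural-log Cmax, AUC0-t and AUC0-∞ for all inference. For the between-dose analysis it fits dose as the single fixed factor, in separate models for IM and SQ, and states: "The 90% CI for the differences in LSmeans for each pairing of doses will be calculated and used to assess relative bioavailability".

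Shell Table 14.2.6.1 carries this through. Its title is "Relative Bioavailability Analysis of Plasma CD388 Pharmacokinetic Parameters" and its rows are the same three raw parameters. The result columns are headed "Dose 1/Dose 2 Difference" and "90% Confidence Interval of Difference", and the only model footnote is "Note: ANOVA model includes dose as fixed factor". It does not state the log scale, a back-transformation or a reference dose.

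The route-comparison shell (Template T2.3, Table 14.2.3.1) is more complete. It names IM as reference and SQ as test, and its footnote reads: "The ratio and 90% confidence interval (CI) were obtained by exponentiating the resulting difference between each comparison of interest".

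SAP Table 5 defines no Cmax/Dose or AUC/Dose.

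**The concern.** Between two different doses, relative bioavailability is about exposure per unit of dose. The ANOVA as written compares total exposure, which rises with dose even when nothing about absorption or clearance changes. A reader who takes the title at face value would read a large non-zero difference as a difference in bioavailability. Because the shell does not say which dose is Dose 1, even the sign of the built-in component is undefined. A real loss of exposure per mg at the higher dose can be hidden, or appear as a gain.

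**Working it through.** The documents give no numerical result for this analysis, so there is no figure to reproduce. The check is algebra, followed by an illustration.

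**Inputs.** Doses by route from SAP Table 2: IM 50, 150 and 450 mg; SQ 50, 150, 450 and 900 mg. CD388 subjects per dose and route: 24/3 = 8 (IM) and 32/4 = 8 (SQ). Model and scale from SAP 7.5.2.

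**Identity.** For any parameter X at doses D1 and D2:

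ln(X1/X2) = ln[(X1/D1)/(X2/D2)] + ln(D1/D2).

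The first term is the dose-normalised contrast and the second is a constant fixed by the design. No PK assumption is used.

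**Constant for each within-route pair, higher dose first:**

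| Pair (mg) | Route | Dose ratio | ln(ratio) |
|---|---|---|---|
| 900 vs 450 | SQ | 2 | 0.693 |
| 150 vs 50 | IM, SQ | 3 | 1.099 |
| 450 vs 150 | IM, SQ | 3 | 1.099 |
| 900 vs 150 | SQ | 6 | 1.792 |
| 450 vs 50 | IM, SQ | 9 | 2.197 |
| 900 vs 50 | SQ | 18 | 2.890 |

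The range is 1.10 to 2.20 for IM and 0.69 to 2.89 for SQ. Signs reverse if the lower dose is Dose 1.

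**Sign example.** If dose-normalised AUC0-∞ at 900 mg were 30% below that at 450 mg, the table would print ln(2 × 0.70) = ln 1.40 = +0.336. The dose-normalised contrast is ln 0.70 = −0.357.

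**Illustration, 450 vs 50 mg, equal exposure per mg.** Assumptions: between-subject CV 30% (the documents give none), 8 subjects per dose, one profile per subject.

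- σ = √ln(1 + 0.30²) = 0.2936; SE = 0.2936 × √(2/8) = 0.1468.
- IM, 24 − 3 = 21 df: half-width 1.7207 × 0.1468 = 0.2526. Printed 2.20 (90% CI 1.94 to 2.45); exponentiated 9.0 (6.99 to 11.59).
- SQ, 32 − 4 = 28 df: half-width 1.7011 × 0.1468 = 0.2497. Printed 2.20 (1.95 to 2.45); exponentiated 9.0 (7.01 to 11.55).
- After normalisation: 1.00 (0.777 to 1.287) IM and 1.00 (0.779 to 1.284) SQ. The log-scale width is unchanged and only the location moves.

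**Sensitivity.** IM at CV 20%: 9.0 (7.59 to 10.67). IM at CV 50%: 9.0 (5.99 to 13.51). Eight per dose is an upper bound for AUC0-∞, because under SAP 7.4 parameters that need λz "will be set to Not Reported (NR) in the Tables and Listings if they meet the following", the criterion being R² below 0.8. With 6 per dose at CV 30%: 9.0 (6.69 to 12.11) IM and 9.0 (6.72 to 12.06) SQ.

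For the smallest offset, SQ 900 vs 450 mg with 8 per dose, the printed interval under equal exposure per mg is 0.44 to 0.94 at CV 30% and 0.29 to 1.09 at CV 50%. Both exclude 0.

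**The case against.** The strongest objection is about meaning. Cohorts 2A to 3B receive two doses of the same strength, so Dose 1 and Dose 2 could be the first and repeat administrations. The constant would then be ln 1 = 0. In support, section 7.5.2 promises individual ratios, which within a subject could only be second over first; the secondary PK objective covers the repeated dose; and the shell has no mg column. This reading does not survive the rest of the text. The SAP sentence refers to each pairing, which implies more than two levels. The model has no subject or period term. Dose means mg in the power model of the same section. The PK shells call the periods single and repeated single, while first-dose and second-dose labels belong to the safety and drug-administration outputs. What stands is that section 7.5.2 does not say which period's profile enters for those cohorts.

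A second objection is that the raw contrasts are valid exposure comparisons and only the label is wrong. In the sign example total exposure does rise 1.4-fold. That is true, and it is why renaming is an acceptable minimum, but under the present title the printed value is not the quantity named.

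Third, the power-model slope and CL/F already give dose-adjusted information. They do, and they are unaffected, but they are separate outputs and do not correct this table.

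Finally, shell appearance may change. That latitude covers layout, footnotes and minor format. It does not extend to the response variable, which section 7.5.2 fixes.

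**Conclusion.** The concern holds. Followed as written, section 7.5.2 and shell Table 14.2.6.1 print the dose-normalised log contrast plus 0.69 to 2.89 in absolute size, under a relative bioavailability heading. The offsets follow from the planned doses alone, on the reading that dose means strength in mg. Only the illustrative intervals depend on the assumed CV, the number of evaluable subjects and one profile per subject.

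The consequence is limited. This is one secondary descriptive table, the SAP ties no margin or decision to it, protocol section 12 plans no formal hypothesis testing, and the same-dose SQ/IM comparison is untouched. It should be fixed because the table is wrong under its own title and the correction is exact.

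**What to change.** In SAP 7.5.2, run this ANOVA on ln(parameter/Dose), or equivalently subtract ln(Dose 1/Dose 2) from each estimate and both confidence limits. Exponentiate, report geometric LSmean ratios with 90% CIs, and state the reference dose for each pair. Relabel shell Table 14.2.6.1 as dose-normalised exposure ratios. Add a footnote that the AUC0-∞ ratio is relative bioavailability only if clearance is the same at both doses, and that the Cmax and AUC0-t ratios are exposure comparisons only. A clause saying that dose means strength in mg, and which dosing period enters for Cohorts 2A to 3B, would remove the remaining ambiguity.

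If the raw contrast is kept, rename it a between-dose exposure comparison in both section 7.5.2 and the shell, and drop the term relative bioavailability.

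The cost is a few sentences in the SAP, one shell relabel with a footnote, and one programming line (none for the rename alone). No new data are needed and no other table changes.
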